6.7. Visit 7 (Day 14 ± 1 day, week 2)

The following procedures and sample collection should be performed at this visit:

1. Record vital signs.
2. Hematology: CBC, including Hb, Hct, RBC count, WBC count, WBC differential and platelet count.

Protocol No.: FP01C-17-001

3. Biochemistry: ALT, AST, ALP, total bilirubin, BUN, Serum Cr, electrolytes (K, Na, Mg, Ca, and P), blood glucose, and lipid profile (LDL, HDL, triglycerides).
4. Collect urine sample for urinalysis test: pH, specific gravity, leukocyte, erythrocyte, urine glucose, nitrate, and protein.
5. Collect serum samples for pharmacokinetics of leuprolide mesylate.
6. Collect serum samples for testosterone and LH.
7. Assess bone pain.
8. Assess urinary signs and symptoms.
9. Record concomitant medication(s).
10. Record AE(s).

6.8. Visit 8 (Day 21 ± 1 day, week 3)

The following procedures and sample collection should be performed at this visit:

1. Record vital signs.
2. Collect serum samples for pharmacokinetics of leuprolide mesylate.
3. Collect serum samples for testosterone and LH.
4. Record concomitant medication(s).
5. Record AE(s).

6.9. Visit 9 (Day 28 ± 1 day, week 4)

The following procedures and sample collection should be performed at this visit:

1. Record vital signs.
2. Perform ECG.
3. Collect blood sample for analysis of:
 - Hematology: CBC, including Hb, Hct, RBC count, WBC count, WBC differential and platelet count
 - Biochemistry: ALT, AST, ALP, total bilirubin, BUN, Serum Cr, electrolytes (K, Na, Mg, Ca and P), blood glucose, lipid profile (LDL, HDL, triglycerides)
 - PSA level
4. Collect serum samples for pharmacokinetics of leuprolide mesylate.
5. Collect serum samples for testosterone and LH.
6. Collect urine sample for urinalysis test:
 - pH, specific gravity, leukocyte, erythrocyte, urine glucose, nitrate, and protein
7. Assess bone pain.
8. Assess urinary signs and symptoms.

Protocol No.: FP01C-17-001

9. Record concomitant medication(s).
10. Record AE(s).

6.10. Visit 10 (Day 42 ± 3 days, week 6-for the first enrolled 30 subjects only)

The following procedures and sample collection should be performed at this visit:

1. Record vital signs.
2. Collect serum samples for pharmacokinetics of leuprolide mesylate.
3. Collect serum samples for testosterone and LH.
4. Record concomitant medication(s).
5. Record AE(s).

6.11. Visit 11 (Day 56 ± 3 days, week 8)

The following procedures and sample collection should be performed at this visit:

1. Record vital signs.
2. Collect serum samples for pharmacokinetics of leuprolide mesylate.
3. Collect serum samples for testosterone and LH.
4. Assess bone pain.
5. Assess urinary signs and symptoms.
6. Record concomitant medication(s).
7. Record AE(s).

6.12. Visit 12 (Day 77 ± 3 days, week 11)

The following procedures and sample collection should be performed at this visit:

1. Record vital signs.
2. Collect serum samples for pharmacokinetics of leuprolide mesylate.
3. Collect serum samples for testosterone and LH.
4. Record concomitant medication(s).
5. Record AE(s).

6.13. Visit 13 (Day 84 ± 1 day; 2nd Dose Administration; week 12)

The following procedures and sample collection should be performed at this visit:

1. Conduct physical examination and record vital signs (including body weight) prior to dosing.
2. Perform ECG prior to dosing and at 4-hour post-dosing.
3. Collect blood sample prior to dosing for analysis of:

Protocol No.: FP01C-17-001

- Hematology: CBC, including Hb, Hct, RBC count, WBC count, WBC differential and platelet count
 - Biochemistry: ALT, AST, ALP, total bilirubin, BUN, Serum Cr, electrolytes (K, Na, Mg, Ca, and P), blood glucose, lipid profile (LDL, HDL, triglycerides)
 - PSA level
 - Collect urine sample prior to dosing for urinalysis: pH, specific gravity, leukocyte, erythrocyte, protein, urine glucose, and nitrate.
4. Collect serum samples for pharmacokinetic analysis of leuprolide mesylate and testosterone prior to dosing and at 2, 4, and 8 hours post-dosing in the first enrolled 30 subjects. Collect serum samples prior to dosing and at 4 hours post-dosing in the remaining 103 subjects for pharmacokinetic analysis of leuprolide mesylate and testosterone.
 5. Collect serum samples for LH prior to dosing.
 6. Assess bone pain prior to dosing.
 7. Assess urinary signs and symptoms prior to dosing.
 8. Record concomitant medication(s) prior to dosing and post dosing.
 9. Record AE(s) prior to dosing and post dosing.
 10. Administer LMIS 25 mg (second administration).
 11. Investigator to assess local injection site reaction post dosing.

6.14. Visit 14 (Day 85 ± 1 day, week 13)

The following procedures and sample collection should be performed at this visit:

1. Record vital signs.
2. Collect serum samples for pharmacokinetics of leuprolide mesylate.
3. Collect serum samples for testosterone and LH.
4. Investigator to assess local injection site reaction.
5. Record concomitant medication(s).
6. Record AE(s).

6.15. Visit 15 (Day 86 ± 1 day; week 13)

The following procedures and sample collection should be performed at this visit

1. Record vital signs.
2. Collect serum samples for pharmacokinetics of leuprolide mesylate.
3. Collect serum samples for testosterone and LH.
4. Investigator to assess local injection site reaction.
5. Record concomitant medication(s).

6. Record AE(s).

6.16. Visit 16 (Day 87 ± 1 day; week 13)

The following procedures and sample collection should be performed at this visit:

1. Record vital signs.
2. Collect serum samples for pharmacokinetics of leuprolide mesylate.
3. Collect serum samples for testosterone and LH.
4. Record concomitant medication(s).
5. Record AE(s).

6.17. Visit 17 (Day 98 ± 3 days, week 14)

The following procedures and sample collection should be performed at this visit:

1. Record vital signs.
2. Collect serum samples for pharmacokinetics of leuprolide mesylate.
3. Collect serum samples for testosterone and LH.
4. Record concomitant medication(s).
5. Record AE(s).

6.18. Visit 18 (Day 112 ± 3 days, week 16)

The following procedures and sample collection should be performed at this visit:

1. Record vital signs.
2. Collect serum samples for pharmacokinetics of leuprolide mesylate.
3. Collect serum samples for testosterone and LH.
4. Assess bone pain.
5. Assess urinary signs and symptoms.
6. Record concomitant medication(s).
7. Record AE(s).

6.19. Visit 19 (Day 126 ± 3 days; week 18 for the first enrolled 30 subjects only)

The following procedures and sample collection should be performed at this visit:

1. Record vital signs.
2. Collect serum samples for pharmacokinetics of leuprolide mesylate.
3. Collect serum samples for testosterone and LH.
4. Record concomitant medication(s).

Protocol No.: FP01C-17-001

5. Record AE(s).

6.20. Visit 20 (Day 140 ± 3 days; week 20)

The following procedures and sample collection should be performed at this visit:

1. Record vital signs.
2. Collect serum samples for pharmacokinetics of leuprolide mesylate.
3. Collect serum samples for testosterone and LH.
4. Assess bone pain.
5. Assess urinary signs and symptoms.
6. Record concomitant medication(s).
7. Record AE(s).

6.21. Visit 21 (Day 161 ± 3 days, week 23)

The following procedures and sample collection should be performed at this visit:

1. Record vital signs.
2. Collect serum samples for pharmacokinetics of leuprolide mesylate.
3. Collect serum samples for testosterone and LH.
4. Record concomitant medication(s).
5. Record AE(s).

6.22. Visit 22 (Day 168 ± 5 days/EOS/ ET; week 24)

The following procedures and sample collection should be performed at this visit:

1. Conduct physical examination (including body weight) and record vital signs.
2. Perform ECG.
3. Collect blood sample for analysis of the following:
 - Hematology: CBC, such as Hb, Hct, RBC count, WBC count, WBC differential and platelet count
 - Biochemistry: ALT, AST, ALP, total bilirubin, BUN, Serum Cr, electrolytes (K, Na, Mg, Ca and P), blood glucose, lipid profile (LDL, HDL, triglycerides)
 - HbA1c
 - PSA level
4. Collect urine sample for urinalysis:
 - pH, specific gravity, leukocyte, erythrocyte, protein, urine glucose, and nitrate
5. Collect serum sample for pharmacokinetics of leuprolide mesylate.
6. Collect serum samples for testosterone and LH.

Protocol No.: FP01C-17-001

7. Assess bone pain.
8. Assess urinary signs and symptoms.
9. Record concomitant medication(s).
10. Record AE(s).
11. Exit off the study (for the 103 subjects without extended PK follow up).
12. For early termination subjects, phone contacts should be performed at 12 weeks after the last injection of investigational product to collect drug-related AE, concomitant medication or non-drug therapy received for AE treatment, disease progression status, and subject survival status.

Subjects who withdraw from the study prematurely for any reason during the study period will undergo the assessments listed for the final End of Study (EOS)/Early Termination (ET) visit. If a subject refuses to return for these assessments or is unable to do so, every effort should be made to contact him or a knowledgeable informant by telephone to determine his condition. Documentation of attempts to contact the subject should be recorded in the medical chart and CRF.

6.23. Visit 23 (Day 182 ± 3 days/PK-extended follow up; week 26)

The following procedures and sample collection should be performed **in the first enrolled 30 subjects only** at this visit:

1. Record vital signs.
2. Collect serum samples for pharmacokinetics of leuprolide mesylate.
3. Collect serum samples for testosterone.
4. Record concomitant medication(s).
5. Record AE(s).
6. Exit off the study (for the first enrolled 30 subjects only).

7. STUDY ASSESSMENTS

7.1. Screening Assessment

7.1.1. Informed consent form

The investigator or designee must explain to each subject the nature of the study, its purpose, the procedures involved, the expected duration, the potential risks and benefits involved and any potential AEs. Each subject will be informed that participation in the study is voluntary and that he can withdraw from participation at any time.

All subjects must provide a signed and dated informed consent at the screening visit prior to dosing LMIS 25 mg. An informed consent form approved by the Institutional Review Board (IRB), Ethics Committee (EC), and/or the applicable health authorities must be used.

7.1.2. Demographics / history

The demographic and baseline characteristics data for all subjects will be collected at the screening visit. The demographics will include date of birth, age, gender, and ethnicity.

The general medical history (including procedural and surgical history, blood donations, and vaccinations) from up to 6 months before the screening visit should be recorded at the CRF. Cancer history should be recorded in a life-time basis.

1. Tumor history should be documented, including:
 - first diagnosis date,
 - histological evidence,
 - TNM classification
 - Staging
 - date of the last relapse or progression (if applicable)
 - previous treatment of malignant disease
 - Surgery
 - Radiation therapy
 - Chemotherapy/immunotherapy
 - Cryotherapy
 - Anti-androgen therapy
 - Other modalities

Whenever possible, diagnoses should be recorded instead of symptoms.

Protocol No.: FP01C-17-001

7.1.3. Eligibility

Eligibility should be thoroughly checked by the investigator at the screening visit. See Section 4.1 and Section 4.2, Inclusion and exclusion Criteria for details.

7.1.4. ECOG performance status

ECOG performance status should be checked at the screening visit and on Day 0. The description of the ECOG performance status scale is as follows:

- 0: Normal activity. Fully active, able to carry on all pre-disease performance without restriction.
- 1: Symptoms, but ambulatory. Restricted in physically strenuous activity, but ambulatory and able to carry out work of a light or sedentary nature (e.g., light housework, office work).
- 2: In bed < 50% of the time. Ambulatory and capable of all self-care, but unable to carry out any work activities. Up and about more than 50% of waking hours.
- 3: In bed > 50% of the time. Capable of only limited self-care, confined to bed or chair more than 50% of waking hours.
- 4: 100% bedridden. Completely disabled. Cannot carry on any self-care. Totally confined to bed or chair.
- 5: Dead

7.2. Efficacy Assessment

Efficacy assessments will be performed based on the study schedule (Table 1a and 1b). The primary endpoint of efficacy is to determine the percentage of subjects with a serum testosterone concentration suppressed to castrate levels (≤ 50 ng/dL) on Day 28 ± 1 day (week 4) following the first injection of LMIS 25 mg, and the proportion of subjects with serum testosterone suppression (≤ 50 ng/dL) from Day 28 ± 1 day (week 4) through Day 168 ± 5 days (week 24) until the end of the study.

The proportion of subjects exhibiting post-suppression breakthrough of serum testosterone to > 50 ng/dL from Day 28 ± 1 day (week 4) through Day 168 ± 5 days (week 24) until the end of the study will also be determined.

The secondary endpoints will determine the mean acute-on-chronic changes in serum testosterone level before injection of the second dose LMIS 25 mg on Day 84 (week 12) and on Days 85, 86, 87 (week 13), and 98 (2 weeks post the second injection). The percentage of subjects observed with acute-on-chronic (surge) effect on serum testosterone and LH levels just before the second dose administration and on Day 1 to Day 3 (Days 85, 86, 87) and 14 days (Day 98) post the second injection of LMIS 25 mg will be analyzed.

The effect of LMIS 25 mg on serum LH levels and the percentage of subjects with enhanced serum testosterone concentration suppression to ≤ 20 ng/dL on Day 28 ± 1 day (week 4) and on Day 168 ± 5 days (week 24) by LMIS 25 mg administration will also be determined. In addition, the effects of LMIS 25 mg on the percentage of subject with PSA relapse and the percentage of subjects that achieves normal serum PSA level will be determined at the end of study.

7.2.1. Hormone level

Serum testosterone will be examined at the screening visit for eligibility (> 150 ng/dL). The screening sample of testosterone for eligibility will be sent to the Central Lab for analysis using a validated commercial assay. Thereafter, the serum testosterone can be sent to the Central Lab for analysis at the investigator's discretion. The serum testosterone will also be measured at baseline (Day 0) and at each visit for analysis at the Bioanalytical Lab. Blood samples will be collected from approximately 133 subjects in the study.

After enrollment, serum testosterone concentration in all subjects will be determined at baseline (Day 0) and at specified time points and will be sent for analysis at the Bioanalytical Lab. Blood samples for serum testosterone concentration measurement will be collected from all 133 subjects in the present study.

Serum testosterone concentrations will be measured by a validated LC/MS/MS method. The method validation follows the European Medicines Agency (EMA) Guideline on Bioanalytical Method Validation (EMA/CHMP/EWP/192217/2009) and the FDA Guidance for Industry: Bioanalytical Method Validation, May 2001.

For a faster sample turn-around, additional serum testosterone samples can also be analyzed by a validated, commercial diagnostic method. Additional testosterone tests (by a commercial method) will be ordered at a routine frequency of no more than monthly, which is consistent with standard medical practice for leuprolide therapy for the purpose of safety monitoring. More frequent tests may be ordered by the investigators at their discretion.

Serum samples for LH concentrations will be analyzed at the BA lab using a validated ELSIA method. More frequent tests of LH may be ordered by the investigators at their discretion, and these samples can be analyzed at the Central Lab for a faster data turn-around.

To establish the extended serum PK/PD relationship between leuprolide and testosterone levels, blood samples for determining the serum testosterone concentrations will be collected in the first enrolled 30 subjects on Day 0 (prior to the first dose of LMIS 25 mg and 2 h, 4 h, and 8 h post dose), Days 1, 2, 3, 7, 14, 21, 28, 42, 56, 77, 84 (week 12: prior to the second dose and 2 h, 4 h, and 8 h post dose), Days 85, 86, 87, 98, 112, 126, 140, 161, 168 (week 24) and Day 182 (week 26).

For determining the serum testosterone concentration in the remaining 103 subjects, blood samples will be collected on Day 0 (prior to the first dose of LMIS 25 mg and 4 hours post dose), Days 1, 3, 14, 21, 28, 56, 77, 84 (week 12: prior to the second dose of LMIS 25 mg and 4 hours post dose), 85, 86, 87, 98, 112, 140, 161, and 168 (week 24/end of study (EOS)).

Blood samples for determining the serum LH concentrations will be collected on Day 0 (prior to the first dose of LMIS 25 mg), Days 1, 2, 3, 7, 14, 21, 28, 42, 56, 77, 84 (week 12, prior to the second dose of LMIS 25 mg), 85, 86, 87, 98, 112, 126, 140, 161, 168 (week 24; end of study) in the first enrolled 30 subjects.

For determining the serum LH concentration in the remaining 103 subjects, blood samples will be collected on Day 0 (prior to the first dose of LMIS 25 mg), Days 1, 3, 14, 21, 28, 56, 77, 84 (week 12: prior to the second dose of LMIS 25 mg), 85, 86, 87, 98, 112, 140, 161, and 168 (week 24/end of study (EOS/ET)).

Protocol No.: FP01C-17-001

Serum samples to the BA Lab will be batched and shipped periodically. Detailed procedures for blood sample collection, processing, and analysis are provided in the Laboratory Manual.

7.2.2. PSA level

The PSA tumor marker will be assessed at specified visit as one of the endpoint assessments in all subjects. Blood samples will be collected at the screening visit, Day 0 (prior to dosing), Day 28 \pm 1 day (week 4), Day 84 \pm 1 (prior to dosing, week 12), and Day 168 \pm 5 days (week 24, EOS/ET). All collected blood samples will be sent to the central laboratory for analysis. More frequent tests may be ordered by the investigators at their discretion.

Detailed procedures for blood sample collection, processing, and analysis are provided in the Laboratory Manual.

7.3. Safety Assessment

7.3.1. Physical examinations and vital signs

Physical examination will be performed in all subjects at the screening visit, Day 84 \pm 1 day (week 12), and Day 168 \pm 5 days (week 24, EOS/ET), by standard physical examination including general appearance, skin, eyes, ear/nose/throat (ENT), head and neck, heart, chest and lungs, abdomen, extremities, lymph nodes, musculoskeletal, neurological, and other body systems if applicable for describing the status of the subject's health.

Changed in physical examinations with clinical significance compared to baseline by principal investigator's judgment will be analyzed.

Height in centimeters (cm) will be measured while the subject is standing after removing his shoes, and the measurement will only be conducted at screening visit. Body weight will be measured at the screening visit, Day 84 (week 12), and Day 168 \pm 5 (week 24, EOS/ET) to the nearest 0.1 kilogram (kg) or pound (lb.) in indoor clothing without shoes.

Vital signs will be measured at each visit, including resting blood pressures, heart rate, respiratory rate, and body temperature.

7.3.2. Local injection site reaction assessment

The specific injection location chosen should be an area with sufficient soft or loose subcutaneous tissue, for example, the upper- or mid-abdominal area. Local AEs have been reported in Eligard[®] studies. The local AEs typically seen with subcutaneously injected products include: transient burning, stinging, and pruritus at the injection site and are typically of mild intensity and brief duration.

The local injection site reaction assessments should include itchiness, erythema, burning and stinging sensation. Assessments will be carried out after investigational product administration and recorded on Day 0, Day 1, Day 2, Day 84, Day 85, and Day 86.

Any local site injection reactions will be captured under AE reporting at the next follow up visit if last longer than 3 days with any severity post LMIS 25 mg administration. The grading for the assessment of local injection reaction is provided in [Table 2](#).

Table 2 Grading of local injection reaction

Grade	Burning/Stinging	Pruritus	Erythema
0 (None)	No stinging / burning	No pruritus	No detectable erythema, skin of normal color
1 (Mild)	Slight warm, tingling sensation; not really bothersome	Occasional, slight itching / scratching	Slight pinkness present
2 (Moderate)	Definite warm, tingling sensation that is somewhat bothersome	Constant or intermittent itching / scratching which is not disturbing sleep	Definite redness, easily recognized
3 (Severe)	Hot, tingling / stinging sensation that has caused definite discomfort	Bothersome itching /scratching which is disturbing sleep	Intense redness

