The administration of LMIS 50 mg significantly reduced the serum PSA levels from the first injection until the end of study in both ITT and PP populations. The mean serum PSA level was reduced by almost 85% and 89%, in ITT and PP populations, respectively, compared to the mean baseline level. The administration of LMIS 50 mg also significantly reduced the mean serum LH levels after the first injection and this effect remained until the end of study. The average serum LH level was significantly reduced by 98% by Day 336 in both ITT and PP populations.

With regard to the safety of LMIS 50 mg in prostate cancer patients, of 137 subjects enrolled, the most common ($\geq 5\%$) TEAEs observed by preferred term was hot flush (48.9%), followed by hypertension (14.6%), pain in extremity (9.5%), injection site pain (7.3%), arthralgia (6.6%), fatigue (6.6%), nocturia (5.8%), back pain (5.1%) and nasopharyngitis (5.1%). With regard to the severity of TEAEs, most TEAEs were mild or moderate. Of 137 enrolled subjects, 62% subjects (85/137) were reported with drug-related AEs determined by investigators. The most common ($\geq 5\%$) drug-related AEs observed by preferred term was hot flush (48.2%), followed by injection site pain (7.3%) and fatigue (5.8%).

There were 3 deaths reported (3/137, 2.2%) in this study. All three fatal events were determined to be unrelated to the use of LMIS 50 mg by investigator. Overall, the administration of LMIS 50 mg demonstrated a tolerable safety profile similar to that of Eligard[®] 45 mg. A 1-year (2 years total exposure) safety extension study of LMIS 50 mg in prostate cancer patients has been initiated and is currently ongoing to follow up on the safety profile of LMIS 50 mg (FP01C-13-001-EX).

Foresee Pharmaceuticals is currently developing leuprolide mesylate 25 mg injectable suspension (LMIS 25 mg) as a line-extension product. Foresee expects that the subcutaneous injection of LMIS 25 mg will be equivalent or similar to the pharmacodynamic effects of the Eligard[®] 22.5 mg 3-month depot formulation in subjects with prostate cancer. The current study is designed to determine the safety, tolerability, and efficacy of LMIS 25 mg for up to 24 weeks of exposure in subjects with prostate cancer. Moreover, the pharmacokinetic profile of serum leuprolide following 2 separate subcutaneous injections of LMIS 25 mg will be evaluated.

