9. SAFETY MONITORING

9.1. Adverse Events

An adverse event (AE) is defined as any untoward medical occurrence in a subject or clinical investigation subject administered a pharmaceutical product which does not necessarily have a causal relationship with the treatment. An AE can therefore be any unfavorable and unintended sign, symptom, or disease temporally associated with the use of a medicinal product, whether or not considered related to the medicinal product. However, abnormal laboratory values or changes are not automatically reported as an AE if they are not clinically significant. They will only be recorded as AEs if a therapeutic action is needed or the investigator judges them to be clinically significant.

The occurrence of AEs should be sought by non-directive questioning of the subject at each visit and/or telephone follow-up during the study. AEs also may be detected when they are volunteered by the subject during or between visits or through physical examination, vital sign measurement, laboratory test or other assessments. All AEs must be recorded on the Adverse Events CRF with the following information:

1. AE term and description
2. Duration (onset and resolution dates or if continuing at final exam)
3. Severity grade (mild, moderate, severe, life-threatening, death)
4. Whether the AE constitutes an SAE
5. Relationship to the study drug (definite/ possible/ unrelated)
6. Action taken and treatment required
7. Outcome (recovered/resolved, recovered/resolved with sequelae, recovering/resolving, not recovered/not resolved, fetal)

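### Protocol 7.3.2 and 9.1 conflict on whether a local reaction of 3 days or less is an AE, so brief injection-site pain, which Table 2 does not grade, can go unrecorded

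*Protocol*

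**What the plan says.** Protocol 7.3.2 fixes the content of the local assessment: "The local injection site reaction assessments should include itchiness, erythema, burning and stinging sensation". Table 2 grades three columns from 0 to 3, headed "Burning/Stinging Pruritus Erythema". It has no column for pain, swelling or induration. The assessments are "recorded on Day 0, Day 1, Day 2, Day 84, Day 85, and Day 86".

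The same section then links local reactions to AE reporting: "Any local site injection reactions will be captured under AE reporting at the next follow up visit if last longer than 3 days". The condition applies at any severity. The section also describes the local events usual after subcutaneous injection as ones that "are typically of mild intensity and brief duration".

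Protocol 9.1 is broader. An AE is "any untoward medical occurrence in a subject or clinical investigation subject administered a pharmaceutical product", and an unintended, unfavorable symptom is enough. Every AE goes on the AE page of the CRF. The one stated exemption is for laboratory changes that are not clinically significant. There is no duration limit.

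SAP 11.5 tabulates the local reaction by Grades 0 to 3 and adds no pain item. SAP 11.1 builds the TEAE tables from AEs that were recorded. SAP section 1 lets the SAP prevail over the protocol where they differ, but the SAP has no rule on this point.

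Protocol 1.3 gives injection-site pain at 7.3% of 137 subjects in the LMIS 50 mg study, both among all TEAEs and among drug-related AEs. It is the only local reaction in either list, and each list stops at 5%.

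**The concern.** A site reading 7.3.2 as its instruction for local reactions finds a duration condition that 9.1 does not contain. For burning, itching or redness little is lost, because the grade is still collected on the local form. For pain, swelling or induration there is no grade, so the AE page is the only place left, and 7.3.2 does not send a short-lived reaction there. The section itself expects local reactions to be brief, so the condition bears on the usual case.

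Injection-site reaction is a listed safety endpoint (Protocol 2.2.2.2), and safety is part of the primary objective (2.1.1). If some sites follow 7.3.2 and others 9.1, the recorded rate of injection-site pain depends partly on which section a site applied. The sponsor had reason to expect this event, since its own 50 mg study reported it.

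**Working it through.** **The rules side by side**

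| Local reaction | Table 2 grade | AE under 7.3.2 | AE under 9.1 |
|---|---|---|---|
| Burning/stinging, pruritus, erythema, 3 days or less | yes | not sent | yes |
| The same, longer than 3 days | yes | yes | yes |
| Pain, swelling, induration, 3 days or less | no | not sent | yes |
| The same, longer than 3 days | no | yes | yes |

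The third row is the gap. There the record exists only if the site applies 9.1.

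**The plan's own figure**

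Inputs: 7.3% and 137 subjects (Protocol 1.3). The count is not printed, so it is recovered from the percentage: 9/137 = 6.57%, 10/137 = 7.30%, 11/137 = 8.03%. Only 10 fits. The exact (Clopper-Pearson) 95% CI for 10/137 is 3.6% to 13.0%.

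**Expected number in this trial**

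Inputs: about 133 planned (Protocol 10.1) and 144 enrolled (SAP 4.4). Assumption: LMIS 25 mg has the 50 mg rate.

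- 133 × 10/137 = 9.7 subjects
- 144 × 10/137 = 10.5 subjects

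The confidence limits widen this: 0.036 × 133 = 4.8 and 0.130 × 144 = 18.7, so roughly 5 to 19.

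**Number that could go unrecorded**

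Let f be the share of pain cases lasting 3 days or less. The documents do not give f, so the full range is shown. The table takes the worst case on the other points: every site follows 7.3.2 and no pain is scored as burning/stinging. The recorded AE rate is (10/137) × (1 − f), and the number unrecorded is N × (10/137) × f.

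| f (assumed) | Recorded AE rate | Unrecorded of 133 | Unrecorded of 144 |
|---|---|---|---|
| 0% | 7.30% | 0 | 0 |
| 25% | 5.47% | 2.4 | 2.6 |
| 50% | 3.65% | 4.9 | 5.3 |
| 75% | 1.82% | 7.3 | 7.9 |
| 90% | 0.73% | 8.7 | 9.5 |
| 100% | 0% | 9.7 | 10.5 |

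**The case against.** The best reply is that the gap closes on a fair reading. Section 7.3.2 says when a local reaction goes to AE reporting; it does not say that shorter ones are excluded. The 3-day sentence stands between the list of assessed symptoms and Table 2, so it can be read as saying when a symptom already graded must also become an AE. Pain is not graded there and would simply follow 9.1.

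Opportunity to record is also good. Protocol 7.3.8 has the investigator ask about AEs at every visit. Table 1a and Table 1b collect AEs at 0, 2, 4 and 8 hours on both dosing days, on Days 1, 2 and 3, and on Days 85 to 87. Some pain may also be scored as burning/stinging, since Grade 3 of that column speaks of definite discomfort.

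Much of this stands. It shows that loss is not inevitable and that the top of the range needs several unfavourable conditions at once. It does not remove the conflict. The sentence in 7.3.2 covers any local reaction, not only the graded symptoms. It is the more specific instruction, and nothing gives 9.1 precedence over it. Frequent questioning helps only if the site regards the answer as reportable. Pain scored as burning/stinging is recorded, but not as pain.

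**Conclusion.** The point holds as a minor one. Sections 7.3.2 and 9.1 give different answers for local reactions of 3 days or less, and for pain, swelling and induration the difference can decide whether there is any record. At the 50 mg rate, 0 to about 10 of 133 to 144 subjects with injection-site pain could be missed. That rests on an equal rate for the 25 mg product, on the undocumented share of short cases, and on how many sites follow 7.3.2. The endpoint is descriptive safety, and the primary efficacy analysis is untouched.

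Three stronger inferences are not supported:

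- A reader might infer that brief pain is bound to be lost because it qualifies as an AE solely when it exceeds 3 days. Section 7.3.2 does not say so, and 9.1 requires it to be recorded.
- A reader might infer that pain is the most frequent local reaction to LMIS 50 mg. Protocol 1.3 lists only AEs at 5% or more and gives no graded rates of burning, itching or erythema.
- A reader might infer that the rule would make 25 mg look better tolerated than 50 mg. The documents do not give the 50 mg study's capture rule, so its 7.3% may have been recorded under the same one, and no comparison of the two products is planned.

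**What to change.** Reconcile 7.3.2 with 9.1 in one or two sentences. State that the 3-day rule applies only to the symptoms graded in Table 2, and that any other local reaction (pain, swelling, induration) is recorded as an AE whatever its duration. No new form is needed. A separate rule for Grade 3 reactions on Table 2 is not required, because SAP 11.5 already tabulates them by grade.

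SAP 4.4 shows 144 subjects already enrolled. If dosing is complete, the wording can no longer change what was collected. The SAP or the report should then state which rule sites applied.

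The cost is small: recorded local AE rates may be higher.
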